9.12 Subgroup analysis

The details of the planned subgroup analyses are presented in 9.4.

9.13 Tables to present

9.13.1 Adjusted logistic regression Model

Coefficients	Odd Ratio	[95% Conf. Interval]	
Treat			
Age			
Sex= F			
Log Troponin x 1000			
Etc			

Table 1: Adjusted results

9.13.2 Unadjusted Logistic regression model

Coefficients	Odds Ratio	[95% Conf. Interval]	
Treat			

Table 2: Unadjusted results

9.13.3 Observed percentage of events

Treatment	Days	N	Events	Cumulative event rate	95% CI Lower bound	95% CI Upper bound
Control	7					
Control	14					
Treatment	7					
Treatment	14					

Table 1

9.14 Figures to present

[figure not shown]

Figure 1

10 Amendments

10.1 Version 1.0

Nil

10.2 Version 2.0

- 1) Addition of an ordinal outcome scale as key secondary endpoint.
- 2) Addition of a longitudinal ordinal model as key secondary analysis.
- 3) Removal of d-dimer and troponin analysis from key interim analysis.

11 REFERENCES

12 Appendix A: Statistical methods for including troponin level and lower detection limit in the model

Troponin assumed to be a strong predictor of the primary outcome thus it might be associated with the other outcomes as well. Troponin levels, both baseline and peak levels will be log transformed and panned to be added to the models using restricted cubic splines using the methods described by Frank Harrell [<https://discourse.datamethods.org/t/comparing-2-biomarkers-using-restricted-cubic-splines-how-to-interpretation-model-building/663/15>].

We assume a proportion of the measurements will be below the lower detection level. Additionally, the lower detection level could be different between the tests used even for the same patients. To overcome this issue four variables will be used:

- Troponin level: log transformed added as restricted cubic splines (*troponin*)
- Detection indicator variable 1: binary, 1 if there is an available measurement, 0 if measurement was taken but it is below the lower detection level (*detected₁*)
- Detection indicator variable 2: binary, 0 if there is an available measurement, 1 if measurement was taken but it is below the lower detection level (*detected₂*)
- Lower detection level: the threshold level of the given test, categorical or continuous depending on the number of different levels (*detection_level*)

These will be added to the model in the following way for both logistic regression and Cox models:

$$Outcome_i = Treatment_i + minimisation\ variables_i + detected_1 * rcs(\log\ troponin, 3) + detected_2 * detection\ level$$

This method will be used for both baseline and peak troponin levels (if used) depending on the aim of modelling.

The first interaction term (*detected₁ * detection_level*) as a non-zero value if there is a detected troponin and in this case the second interaction term is always zero.

The interaction term (*detected₂ * detection_level*) has a non-zero value if troponin was below the detection level and in this case the first interaction term is always zero. This term will show the role of detection level if “not detected” associated with the outcome. The range of the coefficients of the different detection levels will show how sensitive is the outcome to the various detection levels.

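### Appendix A's troponin formula has no stand-alone detection term, so with a continuous or reference-coded detection limit the troponin adjustment depends on a reporting unit that the SAP does not fix

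*SAP*

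**What the plan says.** Section 9.8 puts baseline log troponin into the primary mortality model in the way Appendix A sets out. Appendix A says the same construction serves the logistic and the Cox models, and section 9.4 lists baseline troponin among the subgroup variables to be tested by interaction with treatment.

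Appendix A defines two complementary indicators. The second, detected2, is "binary, 0 if there is an available measurement, 1 if measurement was taken but it is below the lower detection level". The detection limit is "the threshold level of the given test, categorical or continuous depending on the number of different levels". After treatment and the minimisation variables, the printed formula adds only "detected_1 * rcs(\log\ troponin, 3) + detected_2 * detection\ level". Neither indicator stands alone.

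The explanation below the formula names the first product as detected1 × detection_level and describes it "as a non-zero value if there is a detected troponin and in this case the second interaction term is always zero". The second product "has a non-zero value if troponin was below the detection level and in this case the first interaction term is always zero". On how the result will be read, the SAP states: "This term will show the role of detection level if “not detected” associated with the outcome". It adds: "The range of the coefficients of the different detection levels will show how sensitive is the outcome to the various detection levels".

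The SAP states no troponin unit. The shell for the adjusted results in section 9.13.1 has a row labelled "Log Troponin x 1000".

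**The concern.** When a covariate is split into a measured part and a below-limit part, the two groups normally each need their own level, because nothing says where the curve for the measured values should meet the risk of the unmeasured. Two products without an indicator supply that meeting point by accident. It falls wherever log troponin equals zero, which is 1 ng/L in one unit and 1000 ng/L in the other.

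Three things are at stake: how well the covariate adjusts, any subgroup p-value for baseline troponin that uses this block, and the detection-limit coefficient, which the SAP intends to interpret. A coefficient that can change sign with the laboratory unit cannot carry that interpretation. Separately, the sentence naming the first product disagrees with the formula above it, so the two cannot both be programmed.

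**Working it through.** **Inputs.** From Appendix A: the two products, the definitions of detected1 (d1) and detected2 (d2 = 1 − d1), and the open choice of coding for the limit L. From section 6.6.1: 3000 patients (25% versus 20% mortality, 90% power, 5% level). From section 9.2: two-sided tests. The SAP gives no figure for this point itself. The trial size used in the simulations does reproduce: 1464 per arm (2928 in total) without continuity correction, 1504 per arm (3008) with it, and 3000 / 0.98 = 3061.2, rounded up to 3062.

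**Step 1: linear predictors.** Let α be the intercept and put the other covariates aside. With continuous L:
- undetected: α + β·L
- detected: α + b1·log T + b2·s(log T), where s is the non-linear spline column, zero below the first knot.

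So α is the log-odds of an undetected patient as L goes to 0. It is also the height, at T = 1 unit, of the straight line the spline follows below its first knot. The unit alone makes these equal.

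**Step 2: change of unit.** From ng/L to µg/L, log T becomes log T − log 1000 = log T − 6.908. The column d1·log T becomes d1·log T − 6.908·d1. The column s is unchanged because the knots shift too, and d2·L is only rescaled. The fit is therefore unit-free exactly when d1 is already a combination of the model's columns.

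**Step 3: does the model contain d1?** Column ranks for intercept plus troponin block, with three limits:

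| Coding of the limit | Rank | Rank, both units joined | d1 contained? |
|---|---|---|---|
| Continuous | 4 | 5 | no |
| Categorical, reference dropped | 5 | 6 | no |
| Categorical, one indicator per limit | 6 | 6 | yes |
| Continuous plus d2 | 5 | 5 | yes |

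With one indicator per limit, the indicators sum to d2 = 1 − d1, so undetected patients have their own levels. A unit change then moves α by 6.908·b1 and every limit coefficient by the same amount the other way. Each coefficient's sign still depends on the unit, but the differences between them do not. This step uses no assumed data.

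**Step 4: one simulated trial.** Assumed, because the SAP gives no values: limits 2/5/10 ng/L, 26% undetected, log-odds slope 0.5 per unit of log troponin, n = 3000. The site effect was omitted.

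| Model | Log-likelihood ng/L; µg/L | Interaction p ng/L; µg/L |
|---|---|---|
| As printed, continuous | −1440.87; −1462.53 | 0.177; 0.312 |
| Plus d2 | −1440.85; −1440.85 | 0.182; 0.182 |
| One indicator per limit | −1439.19; −1439.19 | 0.141; 0.141 |

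As printed, the limit's coefficient was +0.061 per ng/L in one unit. In the other it was −52.5 per µg/L, that is −52.5 / 1000 = −0.0525 per ng/L.

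**Step 5: 300 simulated trials, 26% undetected, continuous limit, true limit–risk relation positive.**
- Log-likelihood: median difference between units 12.5.
- Interaction p-value: median difference 0.11.
- Limit coefficient negative: 1% (ng/L) and 75% (µg/L) as printed; 5% in either unit with d2 added.
- With a true interaction of 0.2 per log unit, rejection at 0.05 was 56% (ng/L) and 47% (µg/L) as printed, and 54% in both with d2. As printed, the two units disagreed at 0.05 in 18% of trials.
- Treatment odds ratio: mean 0.780 and 0.781; largest change about 0.03 on the log scale.

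**Step 6: other assumptions.** With 52% undetected, the coefficient was negative in 0% (ng/L) and 6% (µg/L). In a single trial with 9% undetected the sign reversed, and p was 0.269 versus 0.471. A separate set with limits 3/5/10 ng/L and about 31% undetected gave mean log-likelihoods of −1453.5 and −1464.0, a median p difference of 0.11, and a negative coefficient in 0.5% versus 48.5% of trials.

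**The case against.** The strongest reply concerns the coding. The appendix permits a categorical limit, and its closing sentence speaks of several coefficients for different limits, which suits one indicator per limit. A dropped reference level would also give zero to undetected patients at that limit, against the statement that the second product is non-zero below the limit. Under one indicator per limit, the shared intercept and the unit dependence of fit and interaction p disappear. This stands, and it makes the point conditional. It does not remove the point, because the continuous form is expressly allowed when there are many limits. Section 6.1 plans about 30 further sites, and Appendix A expects limits to differ between tests.

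A second reply is that an asterisk in model-formula notation implies main effects as well. The text does not bear this out: it describes plain products that vanish in the other group.

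Third, the large figures come from µg/L. The shell's factor of 1000 could mean a conversion to ng/L, the benign case. It could equally mean 1000 times the log, which shifts nothing. In ng/L the printed formula loses under 1 log-likelihood unit and, in step 5, had the wrong sign less often than the repaired one (1% against 5%). That also stands. The ng/L advantage is not general, though: where undetected patients were simulated at lower risk than the curve implies, the wrong sign appeared in 19–53% of trials as printed and 12–15% with the extra term.

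Finally, section 9.4 treats subgroup p-values as hypothesis generating and does not say that the whole Appendix A block is multiplied by treatment. The subgroup consequence therefore holds only for a test that uses this block.

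**Conclusion.** The point holds conditionally. With a continuous limit, or a categorical one with a reference dropped, the printed formula ties detected and undetected patients to one intercept at a place set by an unstated unit. That is algebra and needs no assumed data. The size does rest on assumption: in the scenarios with 26% or about 31% undetected the loss was roughly 10 to 13 log-likelihood units in µg/L, with a median change of 0.11 in the interaction p-value. In ng/L the distortion is small.

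A reader might infer more than this in three ways, and the SAP does not support any of them:
- **That the formula is wrong under every coding.** It is not; one indicator per limit leaves fit and interaction p unit-free.
- **That the limit's coefficient will have the wrong sign.** Reversal is possible, not certain, and was rare with 52% undetected.
- **That the primary result is at risk.** The treatment odds ratio was practically unchanged.

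The misnamed first product is a plain contradiction whatever the coding. Limits, share undetected and slope are assumptions, and the site effect was left out of the simulations.

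**What to change.** In Appendix A:
1. Whenever the limit is continuous or reference-coded, add the indicator: treatment + minimisation variables + detected2 + detected1 × rcs(log troponin, 3) + detected2 × detection level. Alternatively, state that one indicator per limit is used with none dropped. That option is less attractive with sparse limits, since some simulated categorical fits were unstable.
2. State the troponin unit, and say what the factor of 1000 in the section 9.13.1 shell means.
3. Correct the sentence after the formula so that the first product is detected1 × rcs(log troponin, 3).
4. If the section 9.4 test multiplies this block by treatment, include treatment × detected2; otherwise that test stays unit-dependent.

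Centring or logging the limit is optional. The coefficient of detected2 should not be interpreted by itself, because its value still moves with the unit.

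The cost is about one degree of freedom in each model, one more in the interaction test, and a few lines of text. No new data are needed.
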